The primary analysis will be the time to clinical progression of BPH (i.e., time to category I). Participants in categories II through IV at the end of the trial will be censored as of the date of their last completed visit. A supportive analysis will be the time to the first occurrence of clinical progression of BPH (category I) or crossover to known invasive therapy (category II). For this analysis, participants in categories III or IV at the end of the trial will be censored as of the date of their last completed visit.

B. Secondary Research Questions

Although time to clinical progression of BPH is the primary outcome of the study, a key secondary objective of the study will include an assessment of:

- 1. The natural history of BPH in a well-defined cohort of men.
- Other secondary objectives of the study will include assessing differences over time between the four treatment groups with regard to:
 - 2. AUA symptom score and impact index
 - 3. Medical Outcomes Study (MOS) 36-Item Short Form Health Survey score
 - Maximal uroflow

C. Subgroup Hypotheses

Other hypotheses concern whether treatment response or progression of disease in the placebo and three treatment arms are the same or different in subgroups classified by:

- 1. AUA symptom score and impact index
- 2. MOS-36 Health Survey score
- Maximal uroflow
- 4. Residual urine
- Prostate volume

D. Substudy - Ultrasound, Biopsy of the Prostate and Hormones

A key feature of this protocol is the inclusion of predetermined tissue biopsies that will be obtained to evaluate the status of the prostate before and after medication in approximately half of the randomized participants. During the biopsy of the prostate, the participants will undergo transrectal ultrasound (TRUS) of the biopsy to assess differences over time between the four treatment groups with regard to prostate

volume. In addition, a serum sample will be forwarded to the diagnostic center for analysis of hormones (testosterone, dihydrotestosterone, and luteinizing hormone).

The purpose of this substudy is to provide additional information regarding the histopathobiology of BPH and to test the existing biomarkers for their prognostic ability regarding response to therapy. Specific studies to be carried out can be divided according to phases of BPH development as follows:

- 7 1. Proliferation: Immunohistochemical localization of MIB-1 nuclear proliferation antigen.

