- 9 2. Differentiation: Immunohistochemical localization of basal cell specific 10 cytokeratin, pancytokeratin, and smooth muscle action; stromal/epithelial ratio 11 will be determined by video-image analysis.
- 12 3. Biosynthesis: Immunohistochemical localization of prostate-specific antigen;
 13 morphometric analysis of epithelial cell height.
- 14 4. Atrophy: In situ terminal deoxynucleotidyl transferase determination of apoptotic cell death.

This list is likely to be modified during the course of the trial as new or additional markers become available. In addition, an attempt will be made to correlate histopathologic changes of the peripheral zone with concurrent changes in the transition zone with the eventual goal of establishing a cause-effect relationship.

Approximately half of the randomized participants will undergo TRUS and biopsy of the prostate with the collection of a serum sample for analysis of hormones. All potential participants undergoing initial evaluation for study eligibility will have TRUS and biopsy presented to them as an important aspect of the clinical trial. Only those participants who refuse to undergo biopsy of the prostate will be offered the option of participation without biopsy. During the initial screening visit, biopsy will not be presented as an "optional test".

1	SECTION 4				
2			Study Design		
3	A.	Ove	rall Design		
4 5 6 7 8 9 10	drug of fou unifor feasil	n which treatm ir and m rec Prec pility o	DPS is a multi-center randomized, placebo-controlled, double-masked clinically heligible participants with BPH will be randomly assigned to either of three ment arms or a placebo control. Participants will be followed for a minimum a maximum of six years, with an average follow-up of five years, assuming cruitment. Seeding the full-scale clinical trial a pilot study was conducted to assess the fithe full-scale trial. For the pilot study, 141 participants were recruited in six ters and were followed for an average of six months (range: 2 to 10 months)		
12	В.	Elig	ibility Criteria		
13 14	rando	Pote mizat	ential participants meeting the following criteria will be eligible for ion:		
15		1.	Male at least 50 years of age.		
16 17		2.	Peak urinary flow rate is at least 4 ml/sec, but not greater than 15 ml/sec, and the voided volume is at least 125 ml.		
18 19		3.	AUA symptom severity score is greater than or equal to 8 and less than or equal to 30.		

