20 21 22 23 24 25 26 27	be given coo the run-in po for a randor The s weeks, inclu within 6 wee	articipants will then be put on a two-week run-in period. The participant will ded medication and instructed to take it for a two-week period. Following eriod, if the participant is not excluded from the study, he will be scheduled nization visit. At this visit, only vital signs will be obtained. Screening period (from SV1 to the randomization visit) will not exceed 6 adding the two-week run-in period. If a potential participant is not randomized eks after SV1, the participant must reenter the screening period in order to ed eligible for randomization.
28	C. Base	eline Evaluation

Baseline Evaluation

29 30 Baseline measurements from the serum samples and sexual function questionnaire will be taken during SV1. Baseline measurements from the health survey

- 1 and prostatitis questionnaires will be taken during SV2. Baseline urinary flow rate,
- 2 PVR, symptom score, and vital signs will be taken during SV2 (measurements taken
- during SV1 will be used only for inclusion/exclusion criteria). Measurements taken at
- 4 the randomization visit will not be used because of their proximity to the potentially
- 5 biasing invasive procedures.

D. Allocation to Treatment Groups

Following a successful baseline period, the participant will be officially randomized. Random assignment of a participant to a treatment arm will use the microcomputer-based randomization component of the remote data management (RDM) system. The participant is officially randomized when the RDM system discloses the participant's five-digit randomization number.

E. Modifying Recruitment Based on Monitoring Prostate Volumes

All randomized participants will have a transrectal ultrasound (TRUS) of the prostate during screening visit #2. Based on this TRUS, the ellipsoid volume of the total gland (in cc) will be recorded and forwarded to the BCC using the remote data management system. The proportion of randomized participants with prostate volumes < 20 cc and > 50 cc will be reviewed by the Recruitment and Retention Subcommittee after 500, 1,000 and 1,500 participants have been randomized. Based on this periodic review, the Subcommittee may modify the recruitment procedures using the following criteria

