Measurements will be collected prospectively through the study at 3 month intervals (except for the first month of follow-up when dose titration of doxazosin will require visits at end-weeks 3, and 4). Serum samples will be taken at 12 months, yearly thereafter, and at the last visit for PSA, chemistry, and hematology analysis (see Appendix E for details of hematology and chemistry analyses). A physical exam and urinalysis (see Appendix E) will be performed yearly and at the last visit. The sexual function (see Appendix C), MOS-36 Health Survey (see Appendix D) and Prostatitis (see Appendix H) questionnaires will be administered yearly and at the last visit. Appendix G gives a follow-up schedule for the full-scale clinical trial.

If the participant does not continue in the study, a major follow-up visit will be conducted at the last patient visit.

During titration visits (e.g., end-weeks 3 and 4), the participant will be examined for vital signs, and will be assessed for compliance to treatment regimen and for adverse events. At each 3-month assessment point, the participant will be examined for vital signs, will receive the AUA symptom questionnaire (Appendix B), will have an analysis of flow rate, and will be assessed for compliance to treatment regimen and for adverse events.

For participants of the biopsy of the prostate substudy, the following procedures are performed at 12 months post-randomization, at the time of the primary outcome

(i.e., clinical progression of BPH) and either at the 5-year follow-up visit or at the last follow-up visit, whichever occurs first: transrectal ultrasound and needle biopsy of the prostate and collection of a serum sample for analysis of hormones. Pilot study participants who are already beyond 5 years of follow-up at the time of implementation of this amended protocol but have not yet reached the last follow-up visit will have a transrectal ultrasound and needle biopsy of the prostate and collection of serum sample for analysis of hormones at the earliest possible scheduled follow-up visit.

For non-participants of the biopsy of the prostate substudy, a transrectal ultrasound will be performed either at the 5-year follow-up visit or at the last follow-up visit, whichever occurs first.

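### Section 3.D states the prostate-volume comparison only for the biopsy substudy, although Sections 5.E and 6.B schedule baseline and closing scans outside it too

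*Protocol*

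**What the plan says.** Section 3.D describes the substudy of ultrasound, biopsy and hormones. Tissue is to be taken "before and after medication in approximately half of the randomized participants", and at the biopsy "the participants will undergo transrectal ultrasound (TRUS) of the biopsy to assess differences over time between the four treatment groups with regard to prostate" volume. The section later repeats: "Approximately half of the randomized participants will undergo TRUS and biopsy of the prostate". Men come to be outside the substudy by their own choice: "Only those participants who refuse to undergo biopsy of the prostate will be offered the option of participation without biopsy".

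Two other sections schedule scans more widely.

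- Section 5.E, baseline: "All randomized participants will have a transrectal ultrasound (TRUS) of the prostate during screening visit #2". Section 5.B agrees, listing TRUS as a general procedure of the second screening visit, ahead of the substudy-only items.
- Section 6.B, closing scan: "For non-participants of the biopsy of the prostate substudy, a transrectal ultrasound will be performed either at the 5-year follow-up visit" or the last visit, whichever is earlier. Substudy men have a scan at the same closing point, and also at 12 months and at the primary outcome.

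The other objectives do not take up the extra scans. Section 3.B compares the four groups over time on AUA score and impact index, MOS-36 and maximal uroflow, not on volume. Section 3.C uses volume only to form subgroups. The examples of repeated-measures endpoints in Section 8.C omit volume.

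**The concern.** The objectives and the visit schedule do not match. The schedule yields a before-and-after volume for men in and out of the substudy, but the one stated treatment comparison of volume is tied to the scan done with the biopsy. Men outside the substudy undergo a closing transrectal procedure whose result serves no stated between-group question.

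An analyst who follows Section 3.D estimates the volume effect on about half the men who could contribute, and only on men who accepted biopsy. An analyst who uses everyone departs from the only volume comparison in the protocol. The text needs reconciling in either case. At stake are the precision of a secondary comparison and how far it extends to men who refuse biopsy.

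**Working it through.** **Inputs**
- Goal of 2,800 men, 700 per group (Section 8.A).
- Substudy share about one half (Section 3.D), so about 350 per group if balanced.
- Loss hazard 5% per year and two-year entry (Section 8.A); entry from December 1995 to November 1997 (Section 10).
- No SD, effect size or power for volume is given. The effect sizes below are assumptions, shown as a range.

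**1. The plan's own sample size.** Hazards 0.0575 and 0.0384 (two-thirds of it), uniform 2-year entry, 6 years in total, two-sided alpha 0.05/3, power 0.80.

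n = [z(alpha/2)·√(2φ(mean hazard)) + z(power)·√(φ1+φ2)]² / (λ1−λ2)²

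Here φ = λ²/P(event) and P(event) = λ/(λ+η) × {1 − [e^(−4(λ+η)) − e^(−6(λ+η))]/[2(λ+η)]}, with η the loss hazard.

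- No losses (η = 0): 616 per group (stated 612).
- η = 0.05: 693 per group (stated 688).

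Both agree to within 1%, so 700 per group is a sound base.

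**2. Share of volume data outside the stated comparison**
- Men, and planned baseline-to-closing pairs: 350/700 = 50%.
- All scheduled scans, not counting those at progression: 2 per non-substudy man against 3 per substudy man, so 2/(2+3) = 40%.
- Post-baseline scans: 1 against 2, so 1/(1+2) = 33%.

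**3. Standard error**
- Upper bound: √(700/350) = 1.41, whatever the SD.
- The revision history places the closing scan for non-substudy men in the update of 13 October 2000, 4.87 years after entry opened and 2.87 years after it closed. Mean loss by then at 5% per year is 1 − [e^(−0.05×2.87) − e^(−0.05×4.87)]/(0.05×2) = 0.175. If those non-substudy men have no closing scan and every substudy man has one, pairs per group are 700 − 350×0.175 = 639. The ratio is √(639/350) = 1.35, and the share of pairs outside the substudy is (639−350)/639 = 45%.

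**4. Power for one pairwise contrast.** Power = Φ(d·√(n/2) − 1.96), two-sided 0.05, with d in SD units:

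| Assumed d | 350 per arm | 700 per arm |
|---|---|---|
| 0.10 | 26% | 46% |
| 0.15 | 51% | 80% |
| 0.20 | 75% | 96% |
| 0.30 | 98% | >99% |

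The difference detectable with 80% power is (1.96+0.84)·√(2/n): 0.21 SD with 350 per arm and 0.15 SD with 700. At alpha 0.05/3 it is 0.24 and 0.17 SD.

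**The case against.** The strongest reply is that the protocol never says volumes from outside the substudy will be left out. Section 3.D says what the scan done with the biopsy is for. Section 5.E gives its own reason for the universal baseline scan, which is monitoring recruitment by prostate size. The closing scan for the remaining men came with a late update, and Section 3.D was not revised to match. On this view it is a lag in wording, and the analysis set is for the statistical analysis plan, which was not available here.

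Much of this stands. A reader might infer that the plan discards half its volume data, but no text excludes those scans; they simply have no stated between-group objective. What remains is that the protocol's objectives name a population for this comparison, and its schedule supports a larger one.

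Other stronger readings also fail.

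- **Bias from self-selection.** Biopsy is accepted or refused before randomization, so the comparison within the substudy remains randomized.
- **Harm to the subgroups by prostate volume.** These use baseline volume, which is scheduled for all randomized men.
- **Over-weighting of men who progress.** The protocol names no method for volume and does not say that scans triggered by the outcome will be pooled with the rest.
- **A closing scan in literally every man.** The abbreviated cancer follow-up in Section 6.B includes no TRUS, so the ratio of 1.41 is an upper bound.

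**Conclusion.** The mismatch is real and limited. Sections 3.D, 5.E and 6.B do not agree on whose volumes answer the treatment question. About half of the planned baseline-to-closing pairs enter no stated treatment comparison. Followed literally, Section 3.D gives a standard error up to 1.41 times larger than the scheduled scans allow, or about 1.35 under the late-update scenario, and leaves out men who refuse biopsy.

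The ratios rest on the 700-per-group goal and an even split of the substudy across groups. The power figures rest on assumed effects: the gain is substantial between 0.10 and 0.20 SD and negligible at 0.30 SD. Nothing here touches the primary endpoint or its sample size.

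**What to change.** Reconcile Section 3.D with Sections 5.E and 6.B.

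- State, as a between-group comparison, the change in TRUS volume from the second screening visit to the scheduled 5-year or last-visit scan, in all randomized men with both scans. Adjust for baseline volume and clinical center, and take account of the time of the closing scan.
- Keep biopsy, hormones and the 12-month volume comparison as substudy analyses.
- Report scans triggered by the primary outcome descriptively.

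The cost is wording only, because every scan is already scheduled. There is a small analytic price. The closing scan falls at the earlier of year 5 or the last visit, so timing varies and men who leave early are scanned early. Under intent-to-treat, the comparison also includes volumes measured after coded medication has stopped or after invasive therapy. A sensitivity analysis addressing both should accompany it.

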SECTION 3 1 2 **Objectives** 3 Α. **Primary Research Questions** 4 The primary objective of MTOPS is to ascertain if medical therapy (finasteride 5 and/or doxazosin) delays or prevents the progression of BPH. The primary outcome will be the time to clinical progression of BPH. Participants will be classified into one of 6 7 four categories: 8 I. Clinical progression of BPH, as defined by one of the following: 9 1. Acute urinary retention (defined in Appendix F). 10 2. Renal insufficiency due to BPH, as indicated by a 50% increase from 11 baseline in serum creatinine to at least 1.5 mg/dL confirmed within 4 12 weeks. 13 Recurrent urinary tract infections or urosepsis (defined in Appendix F). 3. 14 4. Incontinence (defined in Appendix F). 15 An increase from baseline in the AUA symptom score index of 4 or more 5. points confirmed 2 to 4 weeks later. 16 17 18 II. Crossover to known invasive therapy, prior to clinical progression (as defined in 19 category I). 20 III. Non-compliance with the coded medication treatment regimen, including participants who elect watchful waiting or open-labeled medical therapy 21 including inhibitor of 5- α -reductase or blocker of α -1 adrenoreceptors. 22 23 IV. Completion of study. 24 Participants classified into category I (clinical progression of BPH) because of acute 25 urinary retention, renal insufficiency due to BPH, recurrent urinary tract infections, urosepsis or incontinence will be taken off coded medication but will continue their 26 27 scheduled follow-up visits, if possible. Participants classified into category I because of 28 an increase in the AUA symptom score will be taken off coded medication at the 29 discretion of the clinical center's principal investigator but will continue their scheduled 30 follow-up visits, if possible. Participants classified into category II (crossover to known 31 invasive therapy) will be taken off coded medication but will continue their scheduled 32 follow-up visits, if possible. Participants classified into category II prior to clinical 33 progression of BPH (category I) will remain classified as category II (i.e., never be classified into category I). Participants classified into category III (non-compliance with 34

the coded medication) will continue to be followed, if possible, and will eventually be classified into either categories I, II, or IV by the end of the trial.

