Participants who elect to receive coded medications at the last follow-up visit scheduled within September 1, 2001 to November 30, 2001 will be assessed for adverse events at 3 months after the last scheduled follow-up visit, and for compliance to treatment regimen and adverse events at a final separation visit. Unused coded medications will be returned to the clinic and treatment group assignment will be disclosed to the participant at the separation visit.

Participants who elect not to receive coded medications at the last follow-up visit will be scheduled for a final separation visit to disclose treatment group assignment.

1. Discontinuation of the Follow-up Protocol

The occurrence or presence of the following will constitute discontinuation of the scheduled follow-up protocol:

- 1. Inactive follow-up. (a) Voluntary withdrawal by the participant, or (b) any condition which, in the opinion of the principal investigator, makes it unsafe for the participant to continue.
- 2. Death.

2. Abbreviated Follow-up Protocol for Prostate and Bladder Cancer

Randomized participants with a diagnosis of prostate cancer who elect "watchful waiting" will continue their coded medication and scheduled follow-up visits. For participants with prostate or bladder cancer that are receiving a known therapy for their prostate cancer or have any bladder-sparing procedure for their bladder cancer (e.g. TURBT), a simplified follow-up protocol will be initiated. This abbreviated follow-up protocol will be limited to the AUA symptom questionnaire (Appendix B) administered at quarterly follow-up visits and the MOS-36 Health Survey (Appendix D) administered at annual follow-up visits. For participants with bladder cancer that undergo a cystectomy for their bladder cancer, the abbreviated protocol will be limited to the MOS-36 Health Survey (see Appendix H) only, administered at annual follow-up visits. Participants with prostate or bladder cancer that enroll in a prostate or bladder cancer study,

respectively, will be handled on a case-by-case basis by the Clinical Review Subcommittee.

C. Participant Management Protocols

1. Blood Pressure Control

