Because of the antihypertensive effect of doxazosin, it is important that participant blood pressure be adequately monitored. Participants will also be assessed for orthostatic hypotension based on supine and standing blood pressure. Orthostatic hypotension is defined as a decrease in the systolic blood pressure of greater than 20 mmHg or a decrease in the diastolic blood pressure of greater than 10 mmHg between the supine and standing positions, or the development of significant postural symptoms.

2. Prostate Specific Antigen

Serum prostate specific antigen (PSA) assays will be performed by the Diagnostic Center at baseline, 12 months and yearly thereafter. The baseline serum PSA collected at screening visit #1 (SV1) will be reported directly back to the corresponding clinical center to determine participant eligibility and need for biopsies prior to randomization.

Follow-up PSA values will be reported by the Diagnostic Center directly to the Biostatistical Coordinating Center (BCC) where the BCC will apply a correcting algorithm prior to reporting the PSA value to the corresponding clinical center. The correction algorithm will be: (1) for participants on placebo or doxazosin only, the PSA value will be multiplied by one and (2) for participants on finasteride only or finasteride plus doxazosin, the PSA value will be multiplied by two plus a correction factor for odd-numbered values. Both the Diagnostic Center and individual clinical centers will remain masked to treatment assignment.

Decisions based on the PSA value concerning the need for additional prostate biopsies, other than those scheduled in the prostate biopsy substudy, will be left to the discretion of the clinical center's principal investigator.

3. Treatment Emergent Adverse Events

Reporting of adverse events will be accomplished by collecting information on adverse experiences at each follow-up visit. Occurrence of an adverse event will be indicated on the standard follow-up visit case report form and detailed on the adverse event report form.

In order to facilitate timely reporting of certain serious adverse events, the Adverse Event Report will be filled out immediately and directed to the BCC, where the BCC medical consultant will serve as the serious adverse event report monitor. It is important to note that all serious adverse events should be reported in this way,

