regardless of whether the adverse event is suspected to be related to study medication. 1 A "serious" adverse event is defined as one which is: 2 3 1. fatal or life threatening 2. permanently disabling 4 5 3. requiring or prolonging inpatient hospitalization 6 4. a congenital anomaly or cancer 7 5. an overdose 8 In accordance with the FDA Guidelines effective April 6, 1998, the following additional category is added to the definition: 9 10 6. important medical events that may not result in death, be life-threatening or require hospitalization if, based on appropriate medical judgement, they 11 may jeopardize the patient and may require medical or surgical 12 intervention to prevent a serious adverse event. 13

1			SECTION 7		
2			Data Processing		
3	A.	Case	e Report Forms (CRFs)		
4		Case	e report forms will be filled out at each visit to collect participant data.		
5	1.	Base	Baseline Forms		
6		1.	Eligibility/Exclusion Inventory		
7 8 9		2.	Screening Visit 1: Medical History, Vital Signs, Physical Examination, Urinary Flow Rates, Local Laboratory Results (Urinalysis and Hematology/Chemistries).		
10		3.	Screening Visit 2: Vital Signs and Urinary Flow Rates.		
11		4.	Randomization Visit: Vital Signs.		
12		5.	Recruitment Source Tracking		
13	2.	Follo	ow-up Forms		
14 15 16		1.	Standard Follow-up Visit Inventory: Vital Signs, Urinary Flow Rates, Compliance, Adverse Events, and Concomitant Medications (administered at every participant visit except for titration visits)		
17 18		2.	Major Follow-up Visit Inventory: Physical Examination and Local Laboratory Results (administered yearly)		
19		3.	Interim Visit Checklist: Vital Signs, Compliance, and Intercurrent Illness.		
20		4.	Missed Follow-Up Visit Report		
21 22		5.	Titration Visit Inventory: Vital Signs, Compliance, Adverse Events (administered at end-weeks 3 and 4 of any titration period)		
23	3.	Othe	er Specific Forms		
24		1.	AUA Symptom Questionnaires		

1		2.	Sexual Function Questionnaire		
2		3.	MOS-36 Health Survey Questionnaire		
3		4.	Prostatitis Questionnaire		
4		5.	PSA Collection Report		
5		6.	TRUS/Biopsy Data		
6		7.	Non-scheduled Biopsy Information		
7		8.	Missed Biopsy Report		
8		9.	Significant Clinical Events		
9		10.	Adverse Event Report		
10		11.	Patient Tracking Information		
11		12.	Medication Run-In Information		
12		13.	Clinic Laboratory Normal Range Report		
13		14.	Clinic Review Committee Report		
14		15.	Prostate Cancer Registry Report		
15		16.	Prior Use of Viagra Report		

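### The abbreviated cancer follow-up (Section 6.B.2) omits the routine adverse-event questioning that Sections 6.C.3 and 7 require at each visit, and does not state coded-drug status

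*Protocol*

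**What the plan says.** Protocol Section 6.B.2 separates three groups of men diagnosed with cancer after randomization.

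- Prostate cancer under watchful waiting: these men "will continue their coded medication and scheduled follow-up visits".
- Prostate cancer under a known therapy, or bladder cancer with a bladder-sparing procedure: "This abbreviated follow-up protocol will be limited to the AUA symptom questionnaire (Appendix B) administered at quarterly follow-up visits", plus the MOS-36 once a year.
- Bladder cancer with cystectomy: "the abbreviated protocol will be limited to the MOS-36 Health Survey (see Appendix H) only, administered at annual follow-up visits".

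Three other places bear on the same men.

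- Section 6.C.3: "Reporting of adverse events will be accomplished by collecting information on adverse experiences at each follow-up visit". Its list of serious adverse events includes "a congenital anomaly or cancer". Serious events are to be reported immediately, whether or not they are thought to be drug-related.
- Section 7.A.2: the Standard Follow-up Visit Inventory, which carries vital signs, flow rates, compliance, adverse events and concomitant medications, is completed at all participant visits, with titration visits as the sole exception.
- Section 3.A, category II: men who cross over to known "invasive therapy) will be taken off coded medication but will continue their scheduled" visits, if possible.

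On drug-related monitoring, Section 6.C.1 says: "Because of the antihypertensive effect of doxazosin, it is important that participant blood pressure be adequately monitored". Section 6.A.2 provides for pill counts.

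**The concern.** The abbreviated schedule is worded as a limit, yet it operates at contacts that the protocol still calls follow-up visits. The general rules attach adverse-event collection and the standard form to exactly such visits and make no exception for cancer. A coordinator seeing one of these men must break one rule or the other, and centers may choose differently.

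Safety is part of the trial's stated purpose (Section 1). If 6.B.2 is followed to the letter, scheduled adverse-event ascertainment ends at a point fixed by a post-randomization event. Non-serious events after that point would go largely unrecorded. Serious ones would be captured only when the site happens to learn of them.

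A second gap concerns treatment. Section 6.B.2 says that watchful-waiting men keep their coded medication and is silent about the others. Their exposure, and therefore the monitoring that should apply to them, cannot be read from the text.

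**Working it through.** The main check is one of consistency between sections; the protocol states no figure to reproduce.

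**Step 1. Are the reduced contacts follow-up visits?** Yes. Section 6.B.2 calls both the quarterly and the annual contacts follow-up visits. The general rules in 6.C.3 and 7.A.2 therefore apply unless 6.B.2 displaces them.

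**Step 2. What does each rule require at those contacts?**

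| Item | 6.B.2, cancer therapy or bladder-sparing procedure | 6.B.2, cystectomy | General rule |
|---|---|---|---|
| AUA questionnaire | quarterly | none | quarterly (6.B) |
| MOS-36 | yearly | yearly | yearly (6.B) |
| Adverse events, routine | not listed | not listed | each follow-up visit (6.C.3; form in 7.A.2) |
| Vital signs | not listed | not listed | each quarterly visit (6.B; form in 7.A.2) |
| Compliance, pill counts | not listed | not listed | 6.A.2, 6.B, 7.A.2 |
| Serious adverse events | not mentioned | not mentioned | immediate, on occurrence (6.C.3) |

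The direct conflict is in the adverse-event row. Section 6.C.1 asks for adequate blood-pressure monitoring but sets no frequency, so 6.B.2 does not contradict it in terms. Pill counts belong to 6.A.2, not to 6.C.

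**Step 3. What survives the limit?** Serious-event reporting follows the event and not the visit calendar. Section 6.B.2 does not restrict it, and it covers deaths. What goes is the asking at scheduled contacts, which 6.C.3 gives as the method of ascertainment.

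**Step 4. Are the men on coded drug?** Section 6.B.2 does not say. Category II takes men off drug after known invasive therapy. No section says whether a cancer procedure counts as such, and the trigger in 6.B.2 is known therapy, which need not be invasive. Where category II does apply, it keeps the scheduled visits going, which again disagrees with a reduced schedule. Section 6.B.1 lets the investigator end follow-up on safety grounds but does not mention the drug.

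**Step 5. Scale, under an assumed rate.** The protocol gives no rate of treated cancer. Assume a hazard h of 0.005 to 0.015 per year, together with the protocol's 2,800 men, uniform entry with 4 to 6 years of follow-up, and a loss hazard λ = 0.05 per year. For follow-up T:

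- total time per man = (1 − e^(−λT))/λ
- probability of entering the reduced schedule = h/(h+λ) × (1 − e^(−(h+λ)T))
- time on it = total time − (1 − e^(−(h+λ)T))/(h+λ)

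At h = 0.010 and T = 5: total time 0.2212/0.05 = 4.424 years; probability (0.010/0.060) × 0.2592 = 0.0432, or 121 men; time on the schedule 4.424 − 0.2592/0.060 = 0.104 years per man, or about 292 person-years in all. Averaging over T from 4 to 6 gives a total of about 12,370 person-years and:

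| h per year | Men | Person-years on reduced schedule | Share |
|---|---|---|---|
| 0.005 | 61 | 149 | 1.2% |
| 0.010 | 121 | 295 | 2.4% |
| 0.015 | 179 | 438 | 3.5% |

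**The case against.** The strongest reply is that 6.B.2 is a specific and openly simplified exception to a general rule, and that the treated men are probably off drug. By saying that only the watchful-waiting men continue medication, the text suggests that the others do not, and category II may remove some of them expressly. The protocol also describes itself as an outline, with procedures detailed in a Manual of Operations that is not at hand. Section 7 lists forms, such as the Prostate Cancer Registry Report and Significant Clinical Events, that might be used for these men.

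Part of this stands. If the men are off drug, the blood-pressure and pill-count concerns largely fall away. But the suggestion about drug status remains an inference, and Section 3.A says so outright where it stops the drug. Section 7.A.2 names its one exception, and it is not cancer. An unseen manual does not remove a conflict between two current sections.

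Three stronger readings are tempting and are not supported.

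- A reader might infer that all adverse-event follow-up ceases. It does not, because immediate serious-event reporting is independent of the schedule.
- A reader might infer that entry to the reduced schedule differs by arm because finasteride affects PSA. Section 6.C.2 has the coordinating center correct those values before masked sites see them, and no figure in the protocol shows a difference in detection.
- A reader might see the same gap in the end-of-study medication period. There, men who elect to receive coded medication "will be assessed for adverse events at 3 months after the last scheduled follow-up visit" and again at the separation visit, and the contents of the dedicated form are not shown.

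**Conclusion.** The point holds as an inconsistency in the current text. Section 6.B.2 cannot be followed together with 6.C.3 and 7.A.2, and its literal effect is to end routine adverse-event ascertainment after a cancer that the protocol itself counts as a serious event. Coded-drug status on the abbreviated schedule is unstated and not reconciled with category II.

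The size is uncertain and probably modest. The range of 1.2% to 3.5% of person-years rests entirely on the assumed cancer rate. It describes time without scheduled adverse-event questioning; it must not be read as time without any adverse-event collection. The concern about blood pressure and compliance depends on the men remaining on drug, which the protocol leaves open. The point deserves correction because the remedy is cheap, but it does not threaten the trial's main safety comparison.

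**What to change.** Reword 6.B.2 so that the limit applies to efficacy and questionnaire procedures, while adverse-event collection on the existing form is kept at the quarterly or annual contacts these men already attend. Then 6.C.3 and Section 7 hold for them as well.

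Reconcile 6.B.2 with 6.A.2, 6.C.1, 6.C.3, Section 7 and the category II rule. State whether men on each abbreviated schedule are on or off coded medication, whether cancer treatment counts as known invasive therapy, and which monitoring follows. Those clinical choices are for the investigators. In the same edit, correct the appendix cited for the MOS-36 in the cystectomy sentence: elsewhere the protocol places that survey in Appendix D and the prostatitis questionnaire in Appendix H.

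The cost is protocol wording and a few more forms for a small number of men. No new visits are needed.
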